- Diagnosis of adult T-cell leukemia (HTLV-1 associated, chronic or acute), peripheral T-cell lymphoma (angioimmunoblastic, hepatosplenic, or not otherwise specified), cutaneous T-cell lymphoma (Stage III or IV, with leukemic involvement or erythrodermia), or T-cell prolymphocytic leukemia (T-PLL)
- Measurable or evaluable disease
- Adequate organ and bone marrow function as defined in the protocol.

Design:

- This is a single institution nonrandomized Phase I dose escalation study evaluating increasing doses of SC rhIL-15 in combination with alemtuzumab using a standard 3 + 3 dose escalation.
- Treatment will include s.c. rhIL015 daily (M-F) weeks 1 and 2 (dose levels 0.5-2mcg/kg/dose), followed by IV alemtuzumab beginning in week 3 (escalating doses followed by standard dosing in weeks 4-6).
 - Up to 30 patients will be enrolled in this study.

Abbreviated Title: SC IL-15 + alemtuzumab in ATL **Version Date:** 09/24/2021

SCHEMA

Cohort	rhIL-15	Treatment			We	eks		
number Dose		1 reatment	1	2	3	4	5	6
Cohort 1	Calcart 1 0 5 mag/lag/daga			—				
Cohort 1 0.5mcg/kg/o	0.5mcg/kg/dose	alemtuzumab			$\downarrow\downarrow\downarrow$			
Calcout 2	0.1.42.1./1./1							
Cohort 2 1 mcg/kg/dose	alemtuzumab			$\downarrow\downarrow\downarrow$				
Cohort 3	2 mcg/kg/dose	rhIL-15	—					
		alemtuzumab			$\downarrow\downarrow\downarrow$			

TABLE OF CONTENTS

PRÉC	IS	2
SCHE	EMA	3
TABI	LE OF CONTENTS	
STAT	TEMENT OF COMPLIANCE	7
1 I	NTRODUCTION	
1.1	Study Objectives	
1.2	Background and Rationale	
2 E	ELIGIBILITY ASSESSMENT AND ENROLLMENT	24
2.1	Eligibility Criteria	24
2.2	Screening Evaluation	26
2.3	Participant Registration and Status Update Procedures	27
2.4	Baseline Evaluation	27
3 5	STUDY IMPLEMENTATION	28
3.1	Study Design	28
3.2	Drug Administration	31
3.3	Dose Modifications	32
3.4	Clinical Monitoring	32
3.5	Study Calendar	36
3.6	Criteria for Removal from Protocol Therapy and Off Study Criteria	41
4 (CONCOMITANT MEDICATIONS/MEASURES	42
4.1	Premedication for alemtuzumab infusions	42
4.2	Premedication for IL-15	42
4.3	Prophylaxis for Virus and/or Pneumocystis	42
4.4		
4.5	Platelets and RBC support	42
4.6	Prohibited Medications	43
5 E	BIOSPECIMEN COLLECTION	43
5.1	Correlative Studies for Research and Special Studies	
5.2		
6 I	DATA COLLECTION AND EVALUATION	
6.1	Data Collection	
6.2	Data Sharing Plans	48

	6.3	Response Criteria	49
	6.4	Toxicity Criteria	55
7	NI	H REPORTING REQUIREMENTS/DATA AND SAFETY MONITORING PLA	N55
	7.1	Definitions	55

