2.3.1 Treatment Assignment Procedures

2.3.1.1 Cohorts

Number	Name	Description
1	Leukemia or lymphoma	Patients with a T-cell leukemia or lymphoma (i.e., chronic or acute HTLV-1 associated ATL; peripheral T-cell lymphoma; cutaneous T-cell lymphoma; or, T-cell prolymphocytic leukemia [up to 30 patients])

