3.1.2 Dose Escalation

Dose escalation will proceed in cohorts of 3 to 6 patients. Patients will not begin treatment at the next higher dose level until all patients treated at the previous dose level have completed the DLT evaluation window and an assessment of DLT has been completed.

Patients will receive s.c. rhIL-15 for the initial period Monday-Friday week 1 and 2. They will be assigned to a dose level sequentially based on their order of entry into the study. The starting dose will be 0.5 mcg/kg/dose and in the absence of dose-limiting toxicities dose escalation will proceed to evaluate dose levels of 1.0 and 2.0 mcg/kg/dose. This initial part of the treatment will be 14 days in length and will be followed by 4 weeks (13 treatments) of alemtuzumab. Only toxicities occurring in this 6-week period will be considered in determining dose escalation. Dose-limiting toxicities are defined in Section 3.1.1. Dose-escalation rules are indicated in the table in Section 3.1.2. As just noted, the first 6 weeks of rhIL-15 and alemtuzumab treatment will be considered in defining criteria for dose escalation and the maximum tolerated dose (MTD).

Dose escalation will proceed in cohorts of 3–6 patients. The MTD is the dose level at which no more than 1 of up to 6 patients experience DLT during the first 6 weeks of treatment, and the dose below that at which at least 2 (of \leq 6) patients have DLT as a result of the drug. If a patient did not experience DLT and did not finish treatment, he or she will not be evaluable for toxicity and will be replaced in the dose level. An additional 3 patients may be enrolled to compensate for inevaluable patients.

Dose escalation table:

Dose Escalation Schedule				
Dose Level	Dose of IND Agent*			

Version Date: 09/24/2021

Dose Escalation Schedule			
Level 1 0.5 mcg/kg/dose			
Level 2 1 mcg/kg/dose			
Level 3 2 mcg/kg/dose			
* Doses are stated as exact dose in units (e.g., mg/m², mcg/kg, etc.) rather than as a percentage.			

Dose-escalation rules:

Number of Patients with DLT at a Given Dose Level	Escalation Decision Rule			
0 out of 3	Enter up to 3 patients at the next dose level			
≥ 2	Dose escalation will be stopped. This dose level will be declared the maximally administered dose (highest dose administered). Up to three (3) additional patients will be entered at the next lowest dose level if only 3 patients were treated previously at that dose.			

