10 STATISTICAL CONSIDERATIONS

The primary objective of this trial is to determine the safety, toxicity profile, DLT and MTD of rhIL-15 administered at escalating doses s.c. in combination with alemtuzumab. There are three planned dose levels (0.5, 1, and 2 mcg/kg/dose s.c.) and one dosing strategy (weeks 1 and 2 Monday-Friday). In week three all patients will receive alemtuzumab: 3 mg on day 1, 10 mg on day 2, 30 mg on day 3 and 30 mg on Day 5 of the study. The therapy with alemtuzumab will be continued on weeks 4, 5 and 6 on a 3 x weekly schedule at 30 mg for a total of 4 weeks (13 treatments) of alemtuzumab.

The determination of MTD follows the 3+3 design in which 3 to 6 patients will be enrolled in each combination of dose level. In the initial cohort (Cohort 1), at least 3 patients will be enrolled to receive 0.5 mcg/kg/dose of rhIL-15. In Cohort 2, patients will be enrolled to receive 1 mcg/kg/dose of rhIL-15; and in Cohort 3 patients will receive 2 mcg/kg/dose of IL-15.

The MTD will be based on the assessment of DLT during the first 6 weeks of treatment and will be defined as the dose level at which less than one-third of patients (0/3 or 0-1/6 patients) treated at that dose experience a DLT, with the next higher dose level demonstrating a one-third or greater number of patients (≥2/3 or ≥2/6 patients) having DLT. If a patient did not experience DLT and did not finish the 6 weeks of therapy, this patient will not be evaluable for determination of the MTD and will be replaced in the dose level. An additional 3 to 6 patients will be enrolled at the MTD or, if no severe or dose-limiting toxicities are encountered, the maximum administered dose of rhIL-15, so that a total of 9 patients will be treated at this dose to better characterize the clinical activity of rhIL-15 in this patient population. Accordingly, if all dose levels are evaluated (6 patients per dose level with 9 total patients at the MTD or maximum administered dose) a maximum of 21 evaluable patients will be enrolled. Similarly, if all dose levels are evaluated, the minimum number of evaluable patients required will be 15. An additional 9 patients may be enrolled to compensate for inevaluable patients; thus, bringing the maximum accrual ceiling to 30.

It is expected that accrual can be completed in 60 months.

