Using this dose escalation scheme, the probability of escalating to the next dose level, based on the true rate of DLT at the current dose, is given by the following table (each group will be considered independently of the other):

True toxicity at a given dose	10%	20%	30%	40%	50%	60%
Probability of escalating	.91	.71	.49	.31	.17	.08

The secondary objectives are first to evaluate the potential antitumor activity of the combination of rhIL-15 and alemtuzumab assessing the clinical response rate and time to progression, Another secondary objective is to characterize the biological effects of rhIL-15 administered with alemtuzumab by FACS analysis to define the percentages and absolute numbers of circulating lymphocytes (T and NK cells) and the T-cell subsets naïve, central and effector memory subsets (based on expression of CD52, CD56, CD4, CD8, CD45RO, CD45RA, CD28, CD95, CD194, and CCR7) by flow cytometry. Finally, a secondary objective is to define the effect of the combination on the plasma levels of proinflammatory cytokines using Mesoscale analysis.

Version Date: 09/24/2021

The secondary objectives of the study include characterize the biological effects of rhIL-15 administered with alemtuzumab on the percentages and absolute number of circulating lymphocytes (T and NK cells) and the T-cell subsets naïve, central and effector memory subsets (based on expression of CD52, CD56, CD4, CD8, CD45 RO, CD45RA, CD28, CD95, CCR7, and CD62L) by flow cytometry, and plasma levels of proinflammatory cytokines. Summary statistics will be reported for these measures and considered exploratory.

The accrual ceiling of 24 participants was determined to include the sample size needed for statistical analysis of the safety, toxicity and maximum tolerated dose in this Phase I trial. It provides for 3 inevaluable participants as well as for an expanded cohort of 9 participants at the maximum tolerated dose.

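### Section 10 gives two accrual ceilings for the same trial, 30 and 24, and Section 3.1.2 does not say whether its allowance of 3 is a total or per dose level

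*Combined protocol and SAP*

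**What the plan says.** Five places in the combined protocol and SAP bear on the enrolment limit.

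- **Section 10, sample-size paragraph.** The maximum case is "6 patients per dose level with 9 total patients at the MTD or maximum administered dose", which the plan totals as 21 evaluable patients. It continues: "An additional 9 patients may be enrolled to compensate for inevaluable patients; thus, bringing the maximum accrual ceiling to 30".
- **Section 10, closing paragraph.** "The accrual ceiling of 24 participants was determined to include the sample size needed for statistical analysis of the safety, toxicity and maximum tolerated dose". The next sentence explains the number: "It provides for 3 inevaluable participants as well as for an expanded cohort of 9 participants at the maximum tolerated dose".
- **Section 3.1.2.** A patient who has no DLT and does not finish treatment "will be replaced in the dose level. An additional 3 patients may be enrolled to compensate for inevaluable patients".
- **Section 2.3.1.1, cohort table.** The single cohort ends with "T-cell prolymphocytic leukemia [up to 30 patients".
- **Précis, Design.** "Up to 30 patients will be enrolled in this study".

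None of this is in an amendment log, and neither ceiling is limited to a stage or subgroup.

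**The concern.** The accrual ceiling is the trial's stated sample size. Section 10 gives it twice with different values, and the two statements describe the same design: the same three dose levels and the same expansion to 9 patients. Only the allowance for inevaluable patients differs, 9 in one and 3 in the other.

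Section 3.1.2, the section used to run the escalation, does not settle the matter, because its 3 has no stated scope. Someone working from Section 3.1.2 and the end of Section 10 could close accrual at 24. Someone working from the Précis, the cohort table or the first part of Section 10 would go to 30.

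At stake is whether the cohorts that determine the MTD and the 9-patient expansion can be completed. No escalation, DLT or stopping rule depends on which ceiling is used.

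**Working it through.** **Inputs**

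- Dose levels: 3 (Section 10: "There are three planned dose levels (0.5, 1, and 2 mcg/kg/dose s.c").
- Evaluable patients in the maximum case: 6 at each of two levels and 9 at the MTD or maximum administered dose (Section 10).
- Evaluable patients in the minimum case with all levels evaluated: 15 (Section 10).
- Inevaluable allowance: 9 or 3 (both Section 10); 3 without scope (Section 3.1.2).
- Expected inevaluable rate and true DLT rates: not stated, so assumed below.

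**Reproducing the plan's figures**

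- Maximum evaluable: 6 + 6 + 9 = 21, as stated.
- Minimum evaluable: 3 + 3 + 9 = 15, as stated.
- First ceiling: 21 + 9 = 30, as stated.
- Second ceiling: 21 + 3 = 24, as stated.
- Section 3.1.2 as a total: 21 + 3 = 24. Per dose level: 21 + 3 × 3 = 30.

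Each sum is correct on its own allowance. The fault is that the two allowances contradict each other. In the maximum case, a ceiling of 24 tolerates 3/24 = 12.5% inevaluable and a ceiling of 30 tolerates 9/30 = 30%.

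**Consequence if all 21 evaluable patients are needed**

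Let X, the number evaluable among N enrolled, be binomial(N, 1 − q), where q is an assumed inevaluable rate, independent between patients. P(X ≥ 21):

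| q | N = 24 | N = 30 |
|---|---|---|
| 5% | 0.97 | >0.99 |
| 10% | 0.79 | >0.99 |
| 15% | 0.50 | 0.99 |
| 20% | 0.26 | 0.94 |
| 30% | 0.04 | 0.59 |

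**How often 21 are needed**

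At each level with true DLT rate p, the probability of passing after 3 patients is (1 − p)³ and after 6 patients is 3p(1 − p)² × (1 − p)³. Otherwise the level fails. The final dose is then expanded to 9, and a second de-escalation is ignored. Probability of each evaluable total:

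| Assumed DLT rates, levels 1/2/3 | 15 | 18 | 21 | 12 or fewer |
|---|---|---|---|---|
| 5/5/10% | 0.71 | 0.24 | 0.02 | remainder |
| 10/15/20% | 0.49 | 0.31 | 0.05 | remainder |
| 10/20/30% | 0.47 | 0.29 | 0.05 | remainder |
| 20/25/30% | 0.35 | 0.20 | 0.05 | remainder |

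If 18 are needed, P(X ≥ 18) for 24 against 30 is 0.99 against >0.99 at q = 10%, 0.81 against >0.99 at 20%, and 0.39 against 0.92 at 30%.

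Averaged over all paths, as a range across the four sets of DLT rates:

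| q | 24 is enough | 30 is enough |
|---|---|---|
| 10% | about 0.99 | >0.99 |
| 20% | 0.90 to 0.93 | >0.99 |
| 30% | 0.69 to 0.77 | 0.95 to 0.97 |

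**The case against.** The intent can be read from the documents. The figure 30 stands in the Précis, in the cohort table and in the only step-by-step derivation; 24 stands once. In Section 3.1.2 the allowance follows directly on replacement within the dose level, so 3 per level is a natural reading, and it gives the 9 in Section 10. None of the sums is wrong, so this is an inconsistency and not a miscalculation.

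The probabilities are also open to challenge. They rest on inevaluable and DLT rates that the documents do not give, and the starkest rows apply only when 21 are needed, which happens in about 2 to 5% of paths. The path averages include early stops needing 12 or fewer. The model requires all 9 patients at the final dose to be DLT-evaluable; Section 10 does count all 21 as evaluable, but it says the expansion is there to describe clinical activity.

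Most of this stands, and it limits the weight of the point. It does not remove the contradiction. The tally in favour of 30 leaves Section 3.1.2 aside; read as a total, that section supports 24. Rates above 12.5% are also plausible on the plan's own terms. Section 3.6.1 ends therapy for progression or for any missed rhIL-15 dose. In the earlier alemtuzumab trial (Section 1.2.2.4), median time to treatment failure was 1.6 months, about 7 weeks, against a 6-week evaluation window. That trial included lymphomatous ATL, which is excluded here, so it is only indicative.

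**Conclusion.** The point holds. Section 10 states two ceilings that differ by 6 patients, and no other text reconciles them. This conclusion rests on the documents and simple addition, and does not depend on the probabilities.

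The weight is that of a reconciliation that should be made. The balance of the text suggests 30 is intended, but the documents do not prove it. With few inevaluable patients, the lower ceiling would rarely matter. From an assumed rate of about 20% upward, it would leave a material chance of not completing the planned cohorts.

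**What to change.** The sponsor should confirm which ceiling is meant. If it is 30:

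1. In Section 10, delete the closing paragraph, or replace it with wording such as: *The accrual ceiling of 30 provides for up to 21 evaluable participants, including 9 at the MTD or maximum administered dose, and up to 9 inevaluable participants.*
2. In Section 3.1.2, give the allowance its scope: 9 in total or 3 per dose level. These are different rules. A total of 9 lets all replacements fall at one level; 3 per level does not. Section 10 should use the same form.
3. Check that the Précis, Section 2.3.1.1, Section 3.1.2 and both places in Section 10 then agree.

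The cost is protocol wording only. No patients are added beyond the 30 already stated in three places, and no dose, DLT or stopping rule changes. Section 8.4 lists changes in study size among the significant amendments to be sent to CTEP, so if the sponsor decides on 24 instead, that route would apply.

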11 COLLABORATIVE AGREEMENTS

11.1 AGREEMENT TYPE

There is an MTA with Division of Cancer Treatment and Diagnosis (DCTD) for the IL-15 (#15-2-0064).

12 HUMAN SUBJECTS PROTECTIONS

12.1 RATIONALE FOR SUBJECT SELECTION

Men and women age 18 years or older of all races and ethnic groups are eligible for this trial if they meet the criteria outlined in Section 2.1. Efforts will be made to extend the accrual to a representative population. However, in a Phase I trial with limited sample size, a balance must be struck between patient safety, considerations and limitations on the number of individuals exposed to potentially toxic or ineffective treatments on the one hand and the need to explore gender, racial, and ethnic aspects of clinical research on the other. If differences in outcome that correlate to gender, racial, or ethnic identity were noted, accrual may be expanded, or additional studies may be performed to investigate those differences more fully. Because there is no significant preclinical information regarding the risk to a fetus or newborn infant, pregnant and/or breastfeeding women will be excluded from participation in this trial. Since s.c. rhIL-15 treatment acts by stimulating the patient's immune system to attack their tumor, patients with HIV, hepatitis B or C that have defective immune systems or immune responses are much less likely to have benefit from this immune-based therapy and are not eligible for this trial.

Adults who are cognitively impaired prior to study entry will not be eligible for the trial because they cannot give informed consent. Some of the subjects could become cognitively impaired because of disease progression or other causes. Patients will be offered the opportunity to assign Durable Power of Attorney (DPA) prior to study entry.

12.2 PARTICIPATION OF CHILDREN

Individuals under the age of 18 years of age are not eligible to participate in this trial. The immune physiology of children and the potential toxicity in this population are felt to be sufficiently different from those of adult patients that a separate protocol, dedicated to pediatric patients, appears warranted. Therefore, children may be the object of a separate protocol once toxicity and a dose range with biological activity are defined in adults.

12.3 PARTICIPATION OF SUBJECTS UNABLE TO GIVE CONSENT

Adults unable to give consent are excluded from enrolling in the protocol. However, re-consent may be necessary and there is a possibility, though unlikely, that subjects could become

Version Date: 09/24/2021

decisionally impaired. For this reason and because there is a prospect of direct benefit from research participation (Section 12.4), all subjects will be offered the opportunity to fill in their wishes for research and care, and assign a substitute decision maker on the "NIH Advance Directive for Health Care and Medical Research Participation" form so that another person can make decisions about their medical care in the event that they become incapacitated or cognitively impaired during the course of the study. Note: The PI or AI will contact the NIH Ability to Consent Assessment Team (ACAT) for evaluation as needed for the following: an independent assessment of whether an individual has the capacity to provide consent; assistance in identifying and assessing an appropriate surrogate when indicated; and/or an assessment of the capacity to appoint a surrogate. For those subjects that become incapacitated and do not have pre-determined substitute decision maker, the procedures described in NIH HRPP SOP 14E for appointing a surrogate decision maker for adult subjects who are (a) decisionally impaired, and (b) who do not have a legal guardian or durable power of attorney, will be followed.

12.4 EVALUATION OF BENEFITS AND RISKS/DISCOMFORTS

The discomforts of the 10-day s.c. injections of rhIL-15 are expected to be the same pain and discomfort from venipuncture for blood drawing. The primary risk to patients participating in this research study is from expected or unforeseen toxicity or biological effects of recombinant human IL-15 as an investigational agent. Patients will be carefully monitored for any adverse events as described in Section 7 and appropriate care provided.

The intent of the study is to evaluate the toxicity of rhIL-15 plus alemtuzumab in this Phase I trial and to find a range of doses and dosing schedules where it has an effect on humans (biological activity). Recently there has been new evidence to suggest that rhIL-15 increases the number and state of activation of NK cells and monocytes. These findings lend additional weight to the notion that the administration of rhIL-15 might be associated with an increase in the ADCC mediated by alemtuzumab that in turn is associated with a longer duration of partial or complete responses of the patient's tumor.

12.5 RISKS/BENEFITS ANALYSIS

The success of this effort cannot be predicted at this time because all patients in this protocol have incurable leukemia and limited life expectancies; the potential benefit is thought to outweigh the potential risks.

This risk/benefit analysis applies to all populations of patients eligible for inclusion in this study, including adults able to consent at enrollment as well as those who may become unable to consent during participation.

12.5.1 Risks Related to Imaging

CT, PET and MRI scans often use a contrast agent. There is a small risk of having a reaction to the contrast and most often include nausea, pain in the vein where the contrast is given, headache, metallic and/ or bitter taste in the mouth and a warm, flushing feeling. Rarely, some people have more severe allergic reactions to the contrast which may include skins rashes, shortness of breath, wheezing or low blood pressure.

MRI scans may also involve the use of gadolinium contrast. Although most of the gadolinium is excreted in urine, FDA recently issued a safety alert that indicates small amounts of gadolinium may remain in the body for months to years. The effects of the retained gadolinium are not clear. At this time, retained gadolinium has not been linked to health risks in people whose kidneys

Version Date: 09/24/2021

work well. People with kidney disease are at risk for a serious reaction to gadolinium contrast called "nephrogenic systemic fibrosis" which has resulted in a very small number of deaths. A blood test of kidney function may be done within the month before an MRI scan with gadolinium contrast.

12.5.2 Risks from Radiation Exposure

The procedures for performing the CT and FDG PET/CT scans will follow clinical policies, no special procedures apply to these additional assessments for research purposes. In summary, subjects may receive an annual maximum radiation exposure from up to eight (8) CT scans of the neck, chest, abdomen, and pelvis, and four (4) FDG PET/CT scans for this study. NOTE: CT is expected to be the imaging of choice; PET/CT may be done concurrently in some instances and is optionally accounted for at a lesser number.

The total additional radiation dose for research purposes will be approximately 15 rem.

